Design and Sample Size: Based on a study in China, we assume that the event rate is 40% with standard care and that the event rate can be reduced to 15% when Ibrutinib is added to standard care for COVID-19. With 60 patients and using a standard group sequential design, there is 82.8% power to detect a reduction in the event rate under the alternative hypothesis and constraining the one-sided type I error to 20%. Power was calculated using a z-test for the difference in two proportions, pooled variance, and adjustment for small sample sizes with the Casagrande-Pike-Smith correction (EAST v6.5; Cytel, Inc). There will be an interim analysis when 50% of randomized patients have been followed for 30 days from registration. The study will be stopped early if at the interim analysis the observed event rate is higher in the ibrutinib arm (Arm A) than in the control arm (Arm B). We will plan to over-accrue by about 10% for a total accrual goal of 66 patients.

Although the actual reduction in the event rate could be larger than 25%, it could also be as low as 20% and still be quite meaningful. Furthermore, there is uncertainty in the event rate of the control arm. For these reasons, we have incorporated increased flexibility at the time of the interim analysis to potentially increase the sample size if conditional power indicates promising results, and will thus implement an adaptive group sequential design (Chen, DeMets, Lan; 2004).

At the interim analysis, there are 4 possible outcomes: 1) the futility criteria are met and the trial stops early; 2) the conditional power is unfavorable ($<50\%$), and enrollment continues to the planned sample size without an increase in sample size; 3) the conditional power is in a promising zone (defined as conditional power $\geq 50\%$ and $< 82.8\%$), and sample size may be re-estimated with the original sample size updated to boost the power to a target of 82.8%, subject to a maximum sample size of 120; or 4) the conditional power is favorable ($\geq 82.8\%$), and enrollment continues to the planned

sample size without an increase in sample size. When using this procedure, no adjustment to the final test statistic or critical value from the original design is required to control the Type I error rate. In addition, if the conditional power is in the promising zone, we can choose not to increase the sample size beyond what was originally planned or by a flexible amount without penalty.

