Operating characteristics using the adaptive group sequential design is presented for four different scenarios:

Scenario 1: Event rates in the ibrutinib and control groups are 15% and 40%

Scenario 2: Event rates in the ibrutinib and control groups are 25% and 50%

Scenario 3: Event rates in the ibrutinib and control groups are 20% and 40%

Scenario 4: Event rates in the ibrutinib and control groups are 30% and 50%

For each scenario, the power and expected sample size is also provided for the standard group sequential design. For example, under Scenario 4, the power of the adaptive group sequential design has increased by 11.7% at the cost of corresponding average sample size increases of 11 patients. It is important to note that under the standard group sequential design, the power would have been only 64.7%. For the adaptive group sequential design, the conditional power falls in the promising zone 21.0% of the time, and for these simulations, the re-estimated sample size on average is 101 resulting in a boost in power to 89.2%.

Operating characteristics were calculated based on 10,000 simulations. For the purposes of the simulations, an efficacy boundary was defined using an alpha-spending function with $\text{Gamma}(-30)$, a very conservative boundary to reflect the absence of an interim stopping rule for superiority. All sample size and power calculations used EAST v6.5 (Cytel, Inc).

Scenario	Interim Outcome	Probability of Interim Outcome	Power Conditional on Interim Outcome	Expected Sample Size
1	Futility	3.5%	0%	30
	Unfavorable	13.1%	71.8%	60
	Promising	13.0%	97.8%	111
	Favorable	70.4%	97.9%	60
	All Trials / GSD*	100%	91.0% / 82.8%	66 / 58
2	Futility	5.0%	0%	30
	Unfavorable	13.8%	62.2%	60
	Promising	16.7%	95.3%	103
	Favorable	64.6%	96.5%	60
	All Trials / GSD	100%	86.8% / 78.7%	66 / 57
3	Futility	8.0%	0%	30
	Unfavorable	19.8%	56.9%	60
	Promising	15.9%	92.1%	112

	Favorable All Trials / GSD	56.3% 100%	94.7% 79.3% / 68.0%	60 66 / 55
4	Futility	9.0%	0%	30
	Unfavorable	19.0%	52.0%	60
	Promising	21.0%	89.2%	101
	Favorable	51.1%	93.7%	60
	All Trials / GSD	100%	76.4% / 64.7%	66 / 55

All based on 10000 Simulations; GSD = standard group sequential design

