Primary Endpoint Analysis: All randomized patients will be included in the primary endpoint analysis and analyzed in the treatment arm to which they were randomized (ITT population). The data will be analyzed using a one-sided Fisher's exact test and a promising signal declared if $p \leq 0.20$ and the event rate is lower in the experimental arm. Since the primary endpoint is to be measured within the first 30 days of registration, we do not expect that primary endpoint information will be missing. However, if there is data missing, the patient will be considered a treatment failure.

Sensitivity analyses include comparison between treatment arm when adjusting for stratification factors and other important variables such as type of cancer or more refined categories of standard of care therapy via logistic regression. If there are events for respiratory failure based on clinical diagnosis without an objective measure and driven solely by resource limitation or if patient has DNI (Do Not Resuscitate) status, a sensitivity analysis will compare arms excluding patients with these events. Sensitivity analyses will be performed for the ITT population and for eligible patients who receive their assigned therapy without a major protocol violation.

Adverse Event Stopping Rules: If there is no concerning safety signal in the lead-in cohort, and the study is able to continue to the randomized component as planned, we have included a plan for comparing toxicity at the interim analyses (first 30 patients across both arms). Accrual will be temporarily suspended to this study and discussion of the data with co-investigators and the data safety monitoring board will occur if we observe adverse events that satisfy the following criteria:

- If the percentage of grade 3/4 all-cause adverse events is at least 15% higher in the ibrutinib arm than in the standard of care arm. This would also include grade 2 hemorrhage if considered significant by the treating physician in collaboration with PI.
- If the percentage of grade 4 all-cause adverse events is at least 15% higher in the ibrutinib arm than in the standard of care arm
- If the percentage of grade 5 treatment-related adverse events is at least 5% higher in the ibrutinib arm than in the standard of care arm

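### The adaptive-design table fits an uncorrected z-type test, while the final test is Fisher's exact and the standard-design column carries a small-sample correction, so its power, zone and gain figures do not describe the planned analysis

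*Combined protocol and SAP*

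**What the plan says.** All of this is in section 13; the synopsis (Statistics/Sample Size Estimate) repeats it.

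- **Design power.** "With 60 patients and using a standard group sequential design, there is 82.8% power" at 40% v 15% and one-sided 20%. The method: "Power was calculated using a z-test for the difference in two proportions, pooled variance, and adjustment for small sample sizes", the adjustment being Casagrande-Pike-Smith (CPS).
- **Interim zones.** At half information the trial stops if the ibrutinib event rate is the higher one. Otherwise conditional power below 50% is unfavorable, 50% to below 82.8% is promising, and 82.8% or more is favorable. Only when "the conditional power is in a promising zone" may the sample grow, up to 120. No test, correction or assumed effect is given for this conditional power.
- **Operating characteristics.** The table gives zone probabilities, power by zone, and adaptive v standard-design power of 91.0/82.8, 86.8/78.7, 79.3/68.0 and 76.4/64.7% for Scenarios 1-4. For Scenario 4 the text says that "the conditional power falls in the promising zone 21.0% of the time" and that adaptation adds 11.7% power for 11 more patients on average.
- **Final analysis.** "The data will be analyzed using a one-sided Fisher's exact test", with a promising signal at p ≤ 0.20.

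**The concern.** Conditional power has meaning only relative to the test that will be applied at the end. Fisher's test needs a larger difference than an uncorrected z-test, so the two can place the same interim data in different zones. They also give different power.

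Two things are at stake. The first is the table, which is the plan's argument for adapting: if its columns rest on different tests, and neither simulated column is Fisher's, the power and the gain are misstated for the planned analysis. The second is the interim rule, where an unblinded sample-size decision would depend on a calculation that is not fixed in advance.

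**Working it through.** **Inputs** (section 13): one-sided alpha 0.20; 30 per arm final and 15 per arm interim (half of 60, 1:1); futility if the observed rate is higher on ibrutinib; cut-offs 50% and 82.8%; cap 120; ibrutinib/control rates 15/40, 25/50, 20/40, 30/50%.

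**1. Reproduce the stated standard-design power.** Take P(Z₁ > 0 and Z₂ > 0.8416), correlation √0.5, pooled null variance, unpooled alternative variance, and CPS-reduced n′ = (n − 1/d)²/n. Scenario 1:
- n′ = (30 − 4)²/30 = 22.53
- s₀ = √(2 × 0.275 × 0.725) = 0.6315; s₁ = √(0.15 × 0.85 + 0.40 × 0.60) = 0.6062
- interim mean = 0.25 × √(22.53/2)/0.6062 = 1.384
- final mean less critical value = 0.25 × √22.53/0.6062 − 0.8416 × 0.6315/0.6062 = 1.081
- joint probability = 82.8%

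All four scenarios give 82.8/78.7/68.0/64.7%, exactly as stated. Without CPS the results are 89.0/85.4/77.1/73.7%. The standard-design column is therefore CPS-corrected.

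**2. Identify the test behind the adaptive rows.** For each of the 16 × 16 interim tables (a v b events of 15), conditional power at the observed rates is

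CP(a,b) = Σ Bin(i; 15, a/15) · Bin(j; 15, b/15) · 1{test rejects at (a+i, b+j) of 30 per arm}.

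Classify at 50% and 82.8% and weight by the scenario rates. Promising trials are enlarged to the smallest size that reaches 82.8%, capped at 120.

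| Futility/unfavorable/promising/favorable, % | Plan | Uncorrected z | Fisher |
|---|---|---|---|
| Scenario 1 | 3.5/13.1/13.0/70.4 | 3.5/12.7/12.2/71.6 | 3.5/16.6/16.3/63.5 |
| Scenario 2 | 5.0/13.8/16.7/64.6 | 5.0/13.9/17.0/64.2 | 5.0/23.1/15.7/56.2 |
| Scenario 3 | 8.0/19.8/15.9/56.3 | 7.7/18.8/15.7/57.8 | 7.7/25.4/18.4/48.5 |
| Scenario 4 | 9.0/19.0/21.0/51.1 | 9.2/18.9/20.9/51.0 | 9.2/30.8/16.1/43.9 |

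Mid-P fits about as well: favorable 70.1/64.1/57.0/50.9%. Power by zone agrees: in Scenario 4 the plan has 52.0% (unfavorable) and 93.7% (favorable). At the z zones, an uncorrected z final test gives 52.7 and 93.6%, and Fisher gives 38.6 and 88.5%.

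**3. Show from the plan's own figures that the two power columns differ in basis.** In Scenario 4 the unfavorable and favorable zones, both at N = 60, contribute 0.190 × 52.0 + 0.511 × 93.7 = 57.8%. For the standard design to total 64.7% on the same test, promising-zone power at N = 60 would be (64.7 − 57.8)/0.210 = 33%. That is below the 52.0% of the unfavorable zone, which holds weaker interim results. The expected sizes show the same split. With 30 patients at a futility stop and 60 otherwise, expected N = 60 − 30f. The tabulated f = 9.0% gives 57.3, but the stated 55 needs f of about 17%.

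**4. Adaptive power by final test.**

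| Scenario | 1 | 2 | 3 | 4 |
|---|---|---|---|---|
| Plan | 91.0 | 86.8 | 79.3 | 76.4 |
| z zones, z final | 91.9 | 87.4 | 81.0 | 76.4 |
| z zones, Fisher final | 88.4 | 83.0 | 75.2 | 69.8 |
| Fisher zones, Fisher final | 88.2 | 81.7 | 74.2 | 67.6 |

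Gain in Scenario 4: stated 76.4 − 64.7 = 11.7 points. On uncorrected z it is 76.4 − 73.6 = 2.8. With a Fisher final test it is 69.8 − 65.7 = 4.1 (z zones) or 67.6 − 65.7 = 1.9 (Fisher zones).

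**5. Zone disagreement, if uncorrected z were used at the interim.** The label differs from Fisher's in 11.9/17.3/15.9/19.0% of trials. Other conventions: 10.0-18.9% with three sparse tables reassigned, 10.9-20.2% at the design rates, 12.6-26.0% with closed-form normal conditional power. Examples: 4 v 7 events is 84.0% (z) and 73.9% (Fisher); 5 v 7 is 57.9% and 43.3%. A continuity-corrected z gives the Fisher zones in every scenario (0% disagreement). A final result of 8 v 12 of 30 shows why: z = (4/30)/0.1217 = 1.10 passes 0.8416, but the corrected z = (3/30)/0.1217 = 0.82 does not, and neither does Fisher.

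**The case against.** The strongest reply is that the plan never says the interim calculation will be an uncorrected z-test. The only z-test it describes carries a small-sample correction, and a continuity-corrected z, its analogue, reproduces the Fisher zones exactly. This stands. A reader might infer that 12-19% of trials will be given the wrong zone; the documents support this only if the calculation that fits the table is the one run at the interim.

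Three other tempting readings also fail.

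- **That the table can come only from a z-test.** Mid-P fits as well. In Scenarios 1 and 3 the z favorable zone misses by 1.2 and 1.5 points, about 2.6 and 3 Monte Carlo standard errors.
- **That the 50% and 82.8% cut-offs are false.** They define zones and do not promise performance. If z zones were used, 11-16% of favorable trials would have Fisher conditional power below 82.8%, and 32-57% of promising trials would fall below 50%. Average Fisher power in the favorable zone would still be 96.2/93.9/90.9/88.5%.
- **That type I error is at risk.** With a Fisher final test the maximum is about 13% with either set of zones, against 20% allowed.

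Enlargement is also optional under the plan, and Fisher zones lower power by 0.2 to 2.2 points. None of this removes the mismatch between the table and the final test.

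**Conclusion.** The concern holds for the table and, conditionally, for the interim rule. With Fisher's test the stated adaptive power is too high by 91.0 − 88.4 = 2.6, 86.8 − 83.0 = 3.8, 79.3 − 75.2 = 4.1 and 76.4 − 69.8 = 6.6 points in Scenarios 1-4 (z zones), and slightly more with Fisher zones. The 11.7-point gain mixes a corrected with an uncorrected test and is about 3 to 4 points on a common one, or about 2 if the zones are Fisher's too. The test for interim conditional power is unspecified, and the choice moves between 0% and roughly 10-26% of trials to another zone.

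This rests on exactly 15 per arm at the interim and 30 per arm at the end (no over-accrual), conditional power at observed rates unless noted, and the enlargement rule above. That the table is uncorrected is inferred from its fit and from the arithmetic in step 3, not from a statement in the plan. The benefit of correcting it is accurate figures and a decision rule consistent with the final test, not more power.

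**What to change.** In the synopsis and in section 13 (Design and Sample Size), state that interim conditional power is computed for the test used at the final analysis. Name any correction, the assumed effect (observed or design rates) and the final N. On N, the synopsis continues to 60 while the accrual goal is 66 and all randomized patients are analyzed. Then regenerate the zone, power and expected-N columns with that test, including the standard-design comparator, and restate the 11.7-point and 11-patient sentence from the new figures.

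The work is a short enumeration program and a few sentences, to be completed before the interim look. The cost is less favourable stated power. If Fisher is kept throughout, somewhat fewer trials are enlarged: in Scenario 4, power is 67.6% v 69.8% and mean N about 61 v 66.

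### The operating-characteristics table compares two designs on different bases: its own rows cap the adaptive power gain at about 3 to 8 points, not the stated 8 to 12

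*Combined protocol and SAP*

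**What the plan says.** Section 13 (Design and Sample Size) plans 60 patients, a one-sided 20% type I error and one interim analysis at half the patients. The trial stops for futility if the observed event rate is higher on ibrutinib. If conditional power is between 50% and 82.8% (the promising zone), the sample size may rise to at most 120. In the other continuing zones it stays as planned, and "no adjustment to the final test statistic or critical value from the original design is required". Power was computed with a pooled z-test and "adjustment for small sample sizes with the Casagrande-Pike-Smith correction".

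A table based on 10,000 simulations then gives, for four scenarios, the probability, power and sample size of each interim outcome, with totals for the adaptive and the standard design. For Scenario 4 (30% against 50%) the text says that "the power of the adaptive group sequential design has increased by 11.7" points, "at the cost of corresponding average sample size increases of 11 patients", and that "under the standard group sequential design, the power would have been only 64.7" percent. The synopsis repeats the table and the text.

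The final test is a one-sided Fisher's exact test. On numbers, the plan says "We will plan to over-accrue by about 10% for a total accrual goal of 66 patients" and "All randomized patients will be included in the primary endpoint analysis".

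**The concern.** The two designs differ in one respect only: what happens after a promising interim result. Trials that are futile, unfavorable or favorable run identically under both. Subtracting the two power totals should therefore give the probability of a promising result times the power added within that zone. The stated differences are too large for the promising rows to supply, and the two designs' expected sample sizes imply different futility rates although the futility rule is the same.

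The table and the Scenario 4 sentence are the quantitative case for allowing up to 120 patients. A reader weighing that option is told it buys 8 to 12 points of power when it buys considerably less.

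**Working it through.** **Inputs** (Section 13 table; probability / power / mean N)

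| Outcome | S1 | S2 | S3 | S4 |
|---|---|---|---|---|
| Futility | 3.5% / 0 / 30 | 5.0% / 0 / 30 | 8.0% / 0 / 30 | 9.0% / 0 / 30 |
| Unfavorable | 13.1% / 71.8% / 60 | 13.8% / 62.2% / 60 | 19.8% / 56.9% / 60 | 19.0% / 52.0% / 60 |
| Promising | 13.0% / 97.8% / 111 | 16.7% / 95.3% / 103 | 15.9% / 92.1% / 112 | 21.0% / 89.2% / 101 |
| Favorable | 70.4% / 97.9% / 60 | 64.6% / 96.5% / 60 | 56.3% / 94.7% / 60 | 51.1% / 93.7% / 60 |
| Power, adaptive / standard | 91.0 / 82.8 | 86.8 / 78.7 | 79.3 / 68.0 | 76.4 / 64.7 |
| Expected N, adaptive / standard | 66 / 58 | 66 / 57 | 66 / 55 | 66 / 55 |

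**1. Reproducing the stated totals.**

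- *Adaptive.* The sum of probability × power gives 91.0 / 86.8 / 79.2 / 76.5%. The sum of probability × N gives 65.6 / 65.7 / 65.9 / 66.0. Both match.
- *Standard.* Take the Casagrande-Pike-Smith correction as an effective size per arm of n' = 30(1 − 1/(30d))², which is 22.53 for d = 0.25 and 20.83 for d = 0.20. Use pooled variance under the null and unpooled under the alternative. Then P(interim difference > 0 and final z > 0.8416), with the interim at half information, is 82.8 / 78.7 / 68.0 / 64.7%, as stated. This calculation has futility of 8.3 / 10.2 / 15.4 / 17.1% and expected N of 57.5 / 56.9 / 55.4 / 54.9.

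Each column reproduces. The problem lies in the comparison.

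**2. What the standard total implies in the promising zone.** Implied power at N = 60 = (standard power − unfavorable and favorable contributions) / P(promising).

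- S1: (82.8 − 78.33) / 0.130 = 34.4%
- S2: (78.7 − 70.92) / 0.167 = 46.6%
- S3: (68.0 − 64.58) / 0.159 = 21.5%
- S4: (64.7 − 57.76) / 0.210 = 33.0%

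The unfavorable rows, also at N = 60 but after a worse interim result, have 71.8 / 62.2 / 56.9 / 52.0%. That ordering is not credible.

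**3. Ceiling on the gain.** Give promising trials at N = 60 at least the unfavorable-zone power. Maximum gain = P(promising) × (promising power − unfavorable power).

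| | S1 | S2 | S3 | S4 |
|---|---|---|---|---|
| Calculation | 0.130 × 26.0 | 0.167 × 33.1 | 0.159 × 35.2 | 0.210 × 37.2 |
| Maximum gain, points | 3.4 | 5.5 | 5.6 | 7.8 |
| Stated gain, points | 8.2 | 8.1 | 11.3 | 11.7 |
| Lowest standard power consistent with the rows | 87.7% | 81.3% | 73.6% | 68.7% |
| Stated standard power | 82.8% | 78.7% | 68.0% | 64.7% |

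The shortfalls of 4.9 / 2.6 / 5.6 / 4.0 points are at least 4 Monte Carlo standard errors in every scenario, even if the standard column was also simulated.

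**4. Futility and sample size.** With the futility rows, the standard design's expected N = 60 − 30 × P(futility) = 59.0 / 58.5 / 57.6 / 57.3, against the stated 58 / 57 / 55 / 55. After rounding, the stated values need futility of at least 5.0 / 8.3 / 15.0 / 15.0%, against 3.5 / 5.0 / 8.0 / 9.0% in the rows. Extra patients = P(promising) × (N − 60) = 6.6 / 7.2 / 8.3 / 8.6, against stated differences of 8 / 9 / 11 / 11.

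**5. Likely cause (inference).** Exact binomial futility with 15 per arm, stopping only if the ibrutinib rate is higher, is 3.5 / 5.0 / 7.7 / 9.2%. That fits the adaptive rows. Exact enumeration with an uncorrected pooled z-test gives adaptive power of 91.9 / 87.4 / 81.0 / 76.3%, within about 2 points of the table. On that same test the standard design has 90.9 / 85.6 / 79.1 / 73.6%. The adaptive column thus looks uncorrected and the standard column corrected, so much of the claimed gain would be the correction.

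**6. Like-for-like check with Fisher's test in both columns** (conditional power at the observed trend, re-estimation to 82.8%, cap 120):

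| | Adaptive, S1 to S4 | Standard, S1 to S4 |
|---|---|---|
| N = 60, interim 15 per arm | 88.5 / 83.0 / 75.3 / 69.7% | 86.6 / 80.1 / 72.2 / 65.7% |
| N = 66, interim 16 per arm | 89.5 / 85.1 / 76.1 / 72.6% | 87.8 / 82.8 / 73.0 / 69.3% |
| N = 66, interim 17 per arm | 89.8 / 85.8 / 76.6 / 73.5% | 88.0 / 83.1 / 73.3 / 69.6% |

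The gain is about 2 to 4 points throughout. Type I error of the adaptive design under Fisher is 12 to 14% at common event rates of 30 to 50%, below the 20% limit.

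**The case against.** The strongest reply is that neither column is wrong by itself. The adaptive totals follow from their rows, the standard totals follow from the method the plan names, and 11.7 points and 11 patients are correct subtractions. That is so, but the text presents the difference as what the adaptation buys, and no label warns that the bases differ.

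The ceiling needs an ordering assumption. Without it, arithmetic alone would allow 12.7 to 18.7 points. But the zones are defined by conditional power, and exact enumeration with the z-test gives 73 to 90% in the promising zone against 53 to 76% in the unfavorable zone. A 50% floor instead gives ceilings of 6.2 / 7.6 / 6.7 / 8.2, still below every stated gain, though in Scenario 2 by only 0.5 point.

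The cause is not proven. Matching the standard column to the decimal depends on the variance choice: pooled throughout gives 81.5 / 77.6 / 67.4 / 64.2%. Stopping on ties would give futility of 8.3 / 10.3 / 15.3 / 17.0%, close to what the standard sample sizes imply, but the written rule stops only when the ibrutinib rate is higher.

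The Fisher check does not reproduce the simulated zones: in Scenario 4 it has 13.8% promising with mean N 119, against 21.0% and 101. Moving the cut-off to match leaves the gain at 4.0 points; always going to 120 with that cut-off gives 5.5. Its size depends on the rule, but it stays well below 11.7.

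The practical effect is also limited. The plan justifies re-estimation by uncertainty in the effect and the control rate, and the increase is optional.

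**Conclusion.** The concern holds. Given the shared rules and the ordering assumption, the gain cannot exceed 3.4 / 5.5 / 5.6 / 7.8 points, against the stated 8.2 / 8.1 / 11.3 / 11.7. The futility rates and expected sample sizes of the two designs do not agree, and the Scenario 4 cost is about 9 patients. The explanation by different tests is inference, and the 2-to-4-point Fisher gain rests on an assumed re-estimation rule.

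This should be fixed, but it does not threaten the trial's validity. Error control and decision rules are unaffected, and the 82.8% base power is conservative for the planned test (86.6% under Fisher at 60 patients).

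**What to change.** Rerun both designs with the same final test (the planned one-sided Fisher's exact test), the same futility rule including the handling of ties, and the number actually to be analysed. The plan should settle whether that is 60 or 66. State these choices and the conditional-power rule under the table. Then replace the table and the Scenario 4 sentences (11.7 points, 11 patients, 64.7%, 89.2%) in Section 13 and in the synopsis. The Fisher figures above are checks, not values to copy.

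The cost is one simulation rerun and text edits in two places. The reported adaptive power and gain will look less favourable. No patients are added, and alpha, the interim rule and the cap of 120 do not change.

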	
 • Measurement of T-cell repertoire and IgM, IgA, IgG response to SARS-CoV-2 over time among patients treated with ibrutinib (Arm A) versus control (Arm B) treatment; • Measurement of epigenetic age, clonal hematopoiesis, and MBL on treatment outcome • Measurement of serial change cytokines including (but not limited to) IL6, IL1B, TNF-alpha, IL-10 serum levels over time among patients treated with ibrutinib (Arm A) versus control (Arm B) treatment
Statistics/ Sample Size Estimate	
Safety Lead-In: 12 patients will be enrolled as part of the safety lead-in cohort. Enrollment to a dose level will stop if 2 of the first 3 evaluable patients or if at least 33% of subsequent evaluable patients (i.e, 2/6, 3/9, or 4/12) have DLT.
 
Randomized Phase 2: Allowing for roughly 10% over-accrual, we plan to randomize 66 high-risk patients with cancer to the two arms of the study in a 1:1 ratio utilizing a permuted block schedule. Randomization will be stratified on age (<60 years vs \geq 60 years) and presence of comorbidities (yes vs no) (comorbidities defined in Appendix C). The primary endpoint is the proportion of randomized patients with respiratory failure or death during hospitalization for COVID-19 infection within 30 days of registration.
 
Based on the study in China, we assume that the event rate is 40% and that it can be reduced to 15% when Ibrutinib is given in addition to standard care for COVID-19. With 60 patients and using a standard group sequential design, there is 82.8% power to detect a reduction in the event rate under the alternative hypothesis and constraining the one-sided type I error to 20%. Power was calculated using a z-test for the difference in two proportions, pooled variance, and adjustment for small sample sizes with the Casagrande-Pike-Smith correction (EAST v6.5; Cytel, Inc). There will be an interim analysis when 50% of randomized patients have been followed for 30 days from registration. The study will be stopped early if at the interim analysis the observed event rate is higher in the ibrutinib arm (Arm A) than in the control arm (Arm B). At the final analysis, data will be analyzed using a one-sided Fisher's exact test and a promising signal declared if $p \leq 0.20$ and the event rate is lower in the experimental arm.

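### Deciding by one-sided Fisher's exact test at p ≤ 0.20 gives an actual maximum type I error of about 13 to 16%, leaving part of the accepted 20% unused and some 2 to 8 points of power untaken

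*Combined protocol and SAP*

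**What the plan says.** Section 13 (Design and Sample Size) assumes a control rate of 40% and an ibrutinib rate of 15%: "we assume that the event rate is 40% with standard care" and "the event rate can be reduced to 15% when Ibrutinib is added to standard care for COVID-19". The design is set up while "constraining the one-sided type I error to 20" percent. On power it says: "With 60 patients and using a standard group sequential design, there is 82.8% power to detect a reduction in the event rate". On method: "Power was calculated using a z-test for the difference in two proportions, pooled variance, and adjustment for small sample sizes", the adjustment being the Casagrande-Pike-Smith correction. At half the patients the trial stops if the observed event rate is higher on ibrutinib. Otherwise the sample size may be raised to at most 120. The accrual goal is 66.

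The decision rule is in Section 13 (Primary Endpoint Analysis): "The data will be analyzed using a one-sided Fisher's exact test and a promising signal declared if" p ≤ 0.20 and the rate is lower on ibrutinib. The synopsis agrees: "At the final analysis, data will be analyzed using a one-sided Fisher's exact test". Neither place gives the actual size of that test.

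**The concern.** With about 30 patients per arm Fisher's test is coarse. It can reject only at certain tables, and a nominal 0.20 can correspond to a true error rate well below 0.20. A one-sided 20% level in a small phase 2 trial is a deliberate trade: more false positives in exchange for power. If the test does not use that allowance, the trial bears the small-sample cost without the full benefit. What is at stake is the chance of recognising an effect, including the 20-point reductions (Scenarios 3 and 4) that the plan itself regards as worthwhile.

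**Working it through.** **Inputs (Section 13).** 1:1 allocation; 60 patients (30 per arm), or 66 (33 per arm) with over-accrual; interim at half; one-sided 0.20; ibrutinib v control rates of 15/40, 25/50, 20/40 and 30/50% in Scenarios 1 to 4.

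**1. Reproducing the stated power.** The Casagrande-Pike-Smith correction turns n per arm into an effective n of (n − 1/d)²/n, where d is the difference in rates. For Scenario 1: (30 − 4)²/30 = 22.53.
- Final look: (d√n − z₀.₈₀√(2p̄q̄)) / √(p₁q₁ + p₂q₂) = (0.25 × 4.747 − 0.8416 × 0.6315)/0.6062 = 1.081. Without an interim look, power is 86.0%.
- Interim look: 0.25 × √(22.53/2)/0.6062 = 1.384.
- Joint probability of passing both (bivariate normal, correlation √0.5): **82.8%**, as stated.

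The same steps give 78.7, 68.0 and 64.7% in Scenarios 2 to 4, matching all the standard-design figures in the table.

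**2. Actual size of the planned test.** Take a common event rate p in both arms. Sum the binomial probabilities of all final tables with one-sided Fisher p ≤ 0.20, removing paths stopped at the interim, and maximise over p.

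| Final arms (interim) | With futility stop | Without |
|---|---|---|
| 30/30 (15/15) | 13.6% | 14.2% |
| 33/33 (16/16) | 13.0% | 13.5% |
| 28/32 (15/15) | 14.3% | 14.8% |
| 31/35 (16/17) | 15.1% | 16.0% |

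The unused share runs from (20 − 16.0)/20 = 20% to (20 − 13.0)/20 = 35%. With re-estimation up to 120 the maximum is about 13.5%, if conditional power is computed under the current trend (an assumption; the plan does not say).

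**3. Exact power, and what a calibrated test gains.** Boschloo's test keeps the Fisher p-value as its statistic, but sets the cut-off so that the maximum size is at most 0.20. Here the cut-off takes no credit for the futility stop. At 30/30 the largest qualifying p-value is 0.26605 (maximum size 18.9%); at 33/33 it is 0.2686 (19.5%). Powers below are with the stop applied.

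| Scenario | Stated, standard design | Fisher 30/30 | Boschloo 30/30 | Gain 30/30 (points) | Gain 33/33 (points) |
|---|---|---|---|---|---|
| 1 | 82.8% | 86.6% | 89.1% | 2.4 | 3.1 |
| 2 | 78.7% | 80.1% | 85.0% | 4.9 | 4.8 |
| 3 | 68.0% | 72.2% | 76.2% | 4.0 | 5.9 |
| 4 | 64.7% | 65.7% | 73.2% | 7.5 | 7.2 |

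Example: 8 of 30 events on ibrutinib against 12 of 30 on control gives Fisher p = 0.206. That is no signal under the plan, but a signal under the calibrated test.

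**4. The cut-off cannot be a fixed number.** A cut-off of 0.28 gives a maximum size of about 19% at 30/30 if the stop is always followed, and gains 3.4, 5.1, 5.3 and 7.6 points. Without the stop its size is 20.2% at 30/30, 20.5% at 33/33, 22.3% at 28/32 and 21.8% at 31/35. Even 0.26605, safe at 30/30, gives 20.6% at 31/35 without the stop.

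**5. The adaptive rows of the table.** The stated adaptive powers are 91.0, 86.8, 79.3 and 76.4%. Exact Fisher enumeration under current-trend conditional power gives 88.5, 83.0, 75.3 and 69.7%, lower by 2.5, 3.8, 4.0 and 6.7 points. An uncorrected z-test gives 91.9, 87.4, 81.0 and 76.3%, close to the stated values. This is indicative only: the assumed rule puts 13.8% of Scenario 4 trials in the promising zone, against 21.0% stated.

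One inconsistency needs no such assumption. In Scenario 4 the stated futility probability of 9.0% implies a standard-design expected size of 60 − 30 × 0.09 = 57.3, but the table gives 55, which implies (60 − 55)/30 = 16.7%. The standard and adaptive figures therefore appear to come from different calculations.

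**The case against.** The strongest reply is that a size below the nominal level is not an error. The 20% is a ceiling, Fisher's test respects it in every configuration checked, and it is a standard prespecified choice for about 60 patients. That stands: error control does not fail, and the point is one of efficiency.

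A reader might infer that the 82.8% belongs to a test the trial will not run, or that the trial is underpowered against its own claim. The documents do not support this. The named small-sample correction is what makes a z-test calculation approximate Fisher's test. Exact Fisher power exceeds the stated standard-design figure in all four scenarios.

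A reader might also take 13.6% as a hard cap. It applies to 30/30 with the stop followed. The plan aims for 66 patients and analyses everyone randomized, so the final split is not known in advance.

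Finally, calibration is harder in an adaptive trial. The plan leaves the size of any increase open, so an exact guarantee over the whole procedure needs a fixed re-estimation rule. That also stands and shapes the fix.

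**Conclusion.** The concern holds as a loss of efficiency. The planned test's maximum type I error is about 13 to 16% against an accepted 20%. A test with the same ceiling gains 2.4 to 7.5 points of power at 30/30 and 3.1 to 7.2 points at 33/33, most in Scenario 4. The size and standard-design power results are exact for the arm splits shown and independent binomial outcomes. The comparison with the adaptive powers depends on an assumed current-trend conditional-power rule and should be read as a reason to recompute the table, not as a measured error. This is worth changing before unblinding, but the trial would remain valid without it.

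**What to change.** Preferred: before unblinding, prespecify Boschloo's exact unconditional test, with the one-sided Fisher p-value as the statistic. Give the algorithm for the cut-off, not a number: computed for the actual final arm sizes, maximum type I error at most 0.20, no reliance on the futility stop. If the cut-off is to cover sample-size increases, fix the conditional-power and re-estimation rule as well.

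Alternative: keep Fisher's test at 0.20, and state its actual maximum size and exact power.

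In either case, recompute the operating-characteristics table in Section 13 and the synopsis with the deciding test in every row, and state the conditional-power rule used.

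Cost: wording in two places and an exact calculation, modest for fixed arm sizes and larger if re-estimation is covered. With the preferred option the false-positive rate rises from about 13 to 14% towards the 20% the plan already accepts. For given arm sizes, a calibrated cut-off above 0.20 keeps every result that would be positive under the current rule.
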